## 7.10 CLINICAL LABORATORY ASSESSMENTS

Blood and urine samples will be collected according to the time points in the schedule of assessments for analysis of the following parameters:

### 7.10.1 Routine CBC

- Frequency of testing: At SV, T12, T22-25, T34-37, T48 or VF
- Includes hemoglobin, hematocrit (HCT), red blood cell (RBC) count, white blood cell (WBC) count, WBC differential count (%), absolute neutrophils count and platelets count.

### 7.10.2 Biochemistry

- Frequency of testing: At SV, T12, T22-25, T34-37, T48 or VF
- Biochemistry profile includes assessment of:

Hepatic function indicators: total and direct bilirubin, alkaline phosphatase, aspartate aminotransferase (AST), alanine aminotransferase (ALT), total protein, LDH

Renal function indicators: BUN, creatinine

Electrolytes: sodium, potassium, chloride, calcium and bicarbonate

Other: glucose (random), cholesterol (total)

### 7.10.3 Coagulation Indices

- Frequency of testing: At the Screening Visit, T12, at least once every 4 weeks between T22-25, T34-37, T48, and VF.
- Prothrombin time (PT) and International Normalized Ratio (INR)

### 7.10.4 Hepatitis B surface antigen (HBsAg)

- Frequency of testing: At SV
- To detect presence of Hepatitis B virus infection

### 7.10.5 PK sample for PRO 140

- Frequency of testing: At T1, T4, T8, T12, T16 and at least once every four weeks between T18-21, T26-29 and T34-37, T42-45 and at T48 and VF visits.

### 7.10.6 Anti-idiotypic antibodies to PRO 140

- Frequency of sample collection: At T1, T4, T8, T12, T16 and at least once every four weeks between T18-21, T26-29 and T34-37, T42-45 and at T48 and VF visits. Additionally, sample will be collected at Virologic Failure Follow-up Visit 1 (VF-FU1) and Non-Virologic Failure Follow-up Visit 2 (NVF-FU2)

### 7.10.7 Serum pregnancy test

- Frequency of testing: At SV

- Only for female subjects of childbearing potential. Childbearing potential is defined as someone who is not surgically sterile or is not more than one year past complete cessation of menstrual cycles.

#### 7.10.8 Urine pregnancy test

- Frequency of testing: At T1 prior to first treatment administration
- A urine sample will be collected from female subjects of childbearing potential. This test will be performed at the study site using a commercially available kit.

#### 7.10.9 Plasma HIV-1 RNA level and TruCount T Assay

- Frequency of testing: At SV, T1, T2, T4, T6, T8, T10, T12, T14, T16 and T17, at least once every four weeks between T18-21, T22-25, T26-29, T30-33, T34-37, T38-41, T42-45, T48 and at VF visits when subject comes to clinic. In addition, blood sample will also be collected at all Virologic Failure Follow-up (VF-FU) Visits or Non-Virologic Failure Follow-up (NVF-FU) Visits.
- To assess antiretroviral therapeutic response to PRO 140 or cART regimen

**Note:** Plasma HIV-1 RNA level will be measured using Human Immunodeficiency Virus 1 (HIV-1), Quantitative, RNA (Taqman® Real-Time PCR) test.

TruCount T Assay includes measurement of Absolute Lymphocytes, CD3 cell count, CD4 cell count, CD8 cell count, CD3%, CD4% and CD8%

#### 7.10.10 HIV-1 Trofile® DNA Assay

- Frequency of testing: At SV, T10, and T48 Visits. In addition, Trofile® DNA may also be collected at VF, VF-6mFU and VF12mFU Visits, if last known HIV-1 RNA level is <1000 copies/mL.
- To assess HIV-1 co-receptor tropism. This test determines eligibility for CCR5 antagonist therapy for patients infected with HIV-1. Only those subjects who have exclusive CCR5-tropic virus will be eligible to participate in this study.
- Unlike the standard Trofile® assay (which uses viral RNA), Trofile® DNA Assay can determine the coreceptor tropism of a patient's HIV-1 strain when the patient's viral load is undetectable.

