### 1.4.2.7 PRO 140\_CD01 Study

PRO 140\_CD01 study (open-label, 43 subjects, multi-center) (12-cohort 1, 28-cohort 2, 3-cohort 3) evaluated the efficacy, safety, and tolerability of PRO 140 monotherapy (350 mg subcutaneous injection weekly for up to 12 weeks) for the maintenance of viral suppression following substitution of antiretroviral therapy in HIV-1 infected patients (with exclusive CCR5- tropic virus). Participants in this study were experienced HIV-infected individuals who were virologically suppressed on combination antiretroviral therapy. Consenting patients were shifted from combination antiretroviral regimen to PRO 140 monotherapy for 12 weeks.

Forty (43) subjects (M/F: 40/3) with median age of 55 years (26-72) and median CD4 T-cell count of 604.5 cells/mm^3 (365-1240) were enrolled in the CD01 study. Overall, twenty-three out of 43 (54%) enrolled subjects completed 12 weeks of PRO140 monotherapy without experiencing virologic failure. Virologic failure was defined as two consecutive HIV-1 RNA levels of  $\geq 400$  copies/mL separated by at least 3 days.

Of the first 40 enrolled subjects enrolled under cohort 1 and cohort 2, three subjects were found to

have Dual/Mixed (D/M) tropism [1 at baseline and 2 at the time of virologic failure] and 37 subjects were found to have exclusive CCR5-tropic virus. A letter of amendment was filed to increase the planned number of subjects from 40 to 43 subjects to compensate for the 3 Dual/Mixed subjects enrolled in the study.

All virologic failure subjects who had available lab data in both studies achieved viral suppression to < 400 HIV-1 RNA copies/mL, as well as viral suppression to 'Non Detectable' or < 50 HIV-1 RNA copies/mL after re-initiation of ART.

The by-subject analysis of PhenoSense® Entry Assay data for PRO140, maraviroc, and AMD3100 shows no significant changes in the post-treatment IC50 and IC90 values were noted when compared with baseline values in virologic failure and non-virologic failure groups of subjects.

Anti-PRO140 antibodies were not identified in any post-treatment sample and data derived from the CD01 study further supports the favorable PRO140 PK profile data generated from both pre-clinical as well as prior Phase 1/2 clinical trials.

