## **1.6 RISKS / BENEFITS ASSESSMENT**

### **1.6.1 Risks/Discomfort to Subjects and Precautions to Minimize Risk**

#### **1.6.1.1 Risks associated with using monotherapy treatment**

Study treatment (PRO 140 350mg or 525mg or 700mg SC injection) may not be effective in achieving a reduction in viral load for all subjects. Such cases could lead to an increased risk of developing drug resistance, opportunistic infections and clinical progression of the disease. As patients will not be receiving concomitant antiretroviral drugs of other antiviral classes, should PRO 140 therapy fail, selection of viral variants with reduced susceptibility to these agents would be unlikely (and was not observed in the PRO 140\_CD 01 or PRO 140\_CD 01-Extension studies).

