#### **1.6.1.9 Theoretical risk for increased severity of West Nile virus infection**

Individuals who lack a functional CCR5 gene are at increased risk for severe infection by West Nile virus (Thompson, 2009) Because of this, treatment with CCR5 co-receptor antagonists poses a theoretical risk for increased severity of West Nile virus infection. However, this concern is mitigated by several factors. First, no increased risk was observed for individuals who possess one functional and one non-functional CCR5 gene, indicating that an intermediate amount of CCR5 is sufficient for defense against West Nile virus (Thompson, 2009). Second, use of CCR5 co-receptor antagonists is unlikely to completely abrogate CCR5 function, and there has been no association reported to date between CCR5 co-receptor use and severe West Nile virus. Additionally, PRO 140 weakly antagonizes the natural activity of CCR5 and thus is less likely to adversely affect immune function. Furthermore, this has not been established to be a risk with maraviroc, the anti-CCR5 drug already FDA-approved for the treatment of HIV.

Collectively, the experience with both IV and SC, simulation modeling and the recent confirmation that a higher concentration of PRO 140 synthesized using a highly efficient CHO cell line can be conveniently and safely administered has resulted in the design of the current study.

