#### 7.10.12 HIV-1 Drug Resistance Assay

a. GenoSure Archive Assay

GenoSure Archive assay provides HIV-1 antiretroviral drug resistance data when standard resistance testing cannot be performed due to inadequate plasma viral load.

- Frequency of sample collection: At SV, T1, and T48. Additionally, at VF, VF-6mFU and VF12mFU Visits, if last known HIV-1 RNA level is <1000 copies/mL.

b. PhenoSense® GT

PhenoSense® GT is a combination resistance test for three classes of antiretroviral drugs (i.e., nucleoside/nucleotide, non-nucleoside, and protease inhibitors), that provides both phenotypic and genotypic results from the same blood sample (viral load  $\geq 500$  copies/mL).

- Frequency of sample collection: At VF, VF-6mFU and VF12mFU Visits, if last known HIV-1 RNA level is >1000 copies/mL.

c. PhenoSense Integrase and GeneSeq Integrase testing

PhenoSense Integrase and GeneSeq Integrase testing will be additionally performed in conjunction with PhenoSense® GT, if subject has past exposure to an integrase or in cases where complex drug resistance patterns is known or suspected.

*Samples for PhenoSense® GT (and PhenoSense Integrase and GeneSeq Integrase testing, if collected) will be stored at Lab and will be analyzed only if subject experiences virologic failure.*

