### 8.2.3 Secondary Exploratory Outcome Measures:

- Measurement of treatment adherence to the PRO 140 monotherapy regimen; this will be assessed using number of missed PRO 140 administrations
- Loss of future drug options

*The first occurrence of intermediate to high level resistance to any one or more of the standard antiretroviral drugs to which the patient's virus was considered to be sensitive at trial entry (i.e. excluding drug resistance present at baseline).*
- Proportion of participants overall and within each treatment group experiencing emerging resistance exhibited by fold increase in maraviroc and PRO 140 FC (Fold Change in IC50 and IC90 relative to wild-type virus) between baseline and the time of virologic failure, as a measure of post-baseline phenotypic resistance

**Note:** *Virologic failure is defined as two (2) consecutive plasma HIV-1 RNA levels of  $\geq 200$  copies/mL.*

**Central Nervous System (CNS) sub-study:** In a subset of participants (n=20):

- Level of HIV-1 RNA in CSF at T1 (prior to first dose of PRO 140), T4 and VF visits
- PRO 140 concentration in CSF at T1 (prior to first dose of PRO 140), T4 and VF visits
- Relationship between PRO 140 concentration in plasma and CSF
- Relationship between PRO 140 concentration in CSF and HIV-1 RNA in CSF
- Relationship between plasma and CSF HIV-1 RNA suppression and HIV disease progression and safety parameters (i.e., adverse events and laboratory abnormalities)

**Genitourinary (GU) sub-study:** In a subset of participants (n=20):

- Level of HIV-1 RNA in genital secretion at T1 (prior to first dose of PRO 140), T4, T16 and VF visits.
- PRO 140 concentration in genital secretion at T1 (prior to first dose of PRO 140), T4, T16 and VF visits.
- Relationship between PRO 140 concentration in plasma and genital secretion
- Relationship between PRO 140 concentration and HIV-1 RNA in genital secretion,
- Relationship between plasma and genital secretion HIV-1 RNA suppression and HIV disease progression and safety parameters (i.e., adverse events and laboratory abnormalities)

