3.2 Secondary outcome measures

3.2.1 Exploratory Outcome Measures

- Measurement of treatment adherence to the PRO 140 monotherapy regimen; this will be assessed using number of missed PRO 140 administrations
- Loss of future drug options

The first occurrence of intermediate to high level resistance to any one or more of the standard antiretroviral drugs to which the patient's virus was considered to be sensitive at trial entry (i.e. excluding drug resistance present at baseline).

 - GenoSure Archive Assay will be performed at Baseline.
 - PhenoSense® GT (PhenoSense Integrase and GeneSeq Integrase testing, if applicable), will be performed at the time of virologic failure.
- Proportion of participants overall and within each treatment group experiencing emerging resistance exhibited by fold increase in maraviroc and PRO 140 FC (Fold Change in IC₅₀ and IC₉₀ relative to wild-type virus) between baseline and the time of virologic failure, as a measure of post-baseline phenotypic resistance
 - The data will be from PhenoSense® Entry Assay

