8.2.4.2 HIV-1 Trofile® DNA/RNA Assay

Data for HIV-1 trofile® DNA/RNA assay will be provided by external vendor Monogram Biosciences. All data will be presented as by-subject listings.

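### A post-baseline change in viral tropism closes the CCR5-antagonist class, yet neither loss of future drug options nor any other outcome summarises it

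*Protocol*

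**What the plan says.** **Entry.** Protocol 3.3.1 requires exclusively R5 virus by Trofile DNA. Protocol 3.3.2 excludes dual/mixed and X4 virus, and subjects who failed a maraviroc regimen. Protocol 7.10.10 states the purpose of the assay: "This test determines eligibility for CCR5 antagonist therapy for patients infected with HIV-1". Protocol 1.6.1.9 refers to "maraviroc, the anti-CCR5 drug already FDA-approved for the treatment of HIV".

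**The outcome.** Protocol 8.2.3 defines loss of future drug options as "The first occurrence of intermediate to high level resistance to any one or more of the standard antiretroviral drugs" to which the virus was sensitive at entry. SAP 3.2.1 assigns GenoSure Archive at baseline, and PhenoSense GT, with integrase tests if applicable, which "will be performed at the time of virologic failure". Protocol 7.10.12 describes PhenoSense GT as a "combination resistance test for three classes of antiretroviral drugs": nucleoside/nucleotide, non-nucleoside and protease inhibitors.

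**Tropism data.** Trofile is scheduled at screening, T10 and T48, and at virologic failure and the 6- and 12-month visits after it (Protocol 7.10.10 and 7.10.11). SAP 8.2.4.2 says of it: "All data will be presented as by-subject listings". SAP 8.2.4.5 treats the Quest tropism assay the same way.

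**The concern.** Protocol 1.6.1.1 argues that, because subjects take no drugs from other classes, "selection of viral variants with reduced susceptibility to these agents would be unlikely". The assays named for loss of future drug options at failure look in those other classes, where the protocol itself expects little. The loss most specific to a CCR5 antibody is a change to virus that no longer depends on CCR5 alone, and it falls outside the outcome.

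A low figure could then be read as showing that a period of monotherapy costs the patient nothing in later treatment choice. The figure would not have tested that for the CCR5 class, although the samples that could test it are collected.

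**Working it through.** The plan states no figure to reproduce, so the check sets the sections side by side.

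1. **Is the class open at entry?** On tropism, yes, for every subject (Protocol 3.3.1, 3.3.2). Maraviroc susceptibility is measured by PhenoSense Entry (Protocol 7.10.13.4) but does not decide entry. The statement is therefore about tropism, not full susceptibility.

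2. **Can the outcome register a tropism change?** The definition requires intermediate to high level resistance. At failure SAP 3.2.1 feeds it with PhenoSense GT and integrase tests, none of which classifies tropism. The documents do not say which classes GenoSure Archive covers, but SAP 3.2.1 uses it here as the baseline reference. A subject who is R5 at screening and dual/mixed later, with no new resistance, counts as no loss.

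3. **Does another outcome register it?** The outcomes in Protocol 8.2.1 to 8.2.4 and SAP 3.1 to 3.2 do not name tropism, and it is not among the six prognostic factors. The nearest is emerging resistance, the fold change in maraviroc and PRO 140 IC50 and IC90. That measures susceptibility between baseline and failure. It gives no tropism class, and it omits non-failures, who have Trofile at T10 and T48.

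4. **Is tropism summarised elsewhere?** SAP 8.2.3 gives summaries for exploratory outcomes, but tropism is not one of them. Within SAP 8.2.4, the neurological, weight and height entries (8.2.4.1, 8.2.4.10, 8.2.4.11) call for a summary as well as a listing. The two tropism entries call for listings only.

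5. **Has such a change been seen?** Protocol 1.4.2.7 reports 3 dual/mixed subjects among the first 40 in CD01: "1 at baseline and 2 at the time of virologic failure". The arithmetic agrees: 40 − 3 = 37 exclusively R5. Yet Protocol 1.5, reviewing the 350 mg weekly data, says that tropism was not altered. The two sections need to be reconciled.

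**The case against.** **The general rule.** SAP 8.1 says that all collected data will be summarised by variable type, and Trofile is categorical. This is the best argument against the point. It does not reliably settle it: the specific tropism entries mention only listings while their neighbours ask for summaries, and a generic frequency table would fix no baseline reference, denominator or definition of change.

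**Partial cover.** The fold-change outcome does address CCR5-class susceptibility, and the iDMC is to monitor post-treatment tropism closely (Protocol Synopsis and 8.5). So tropism is neither ignored nor unreported. But one measure is not tropism, and the other is monitoring rather than a reported outcome.

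**The wording.** Any standard antiretroviral could be read to include maraviroc. The definition still requires resistance, and SAP 3.2.1 assigns it no entry or tropism assay.

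**The status.** The outcome is exploratory and the SAP plans no inferential statistics (SAP 7.3, 7.4). This stands. The point concerns how a result will be read, not a decision rule.

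**Two stronger readings.** A reader might scale the CD01 count to about 500 subjects. The documents do not support that. They do not say how many CD01 subjects had a post-baseline tropism test, and CD01 ran 12 weeks at 350 mg with a failure threshold of 400 copies/mL, against 48 weeks, three doses and 200 copies/mL here. A reader might also count any single dual/mixed result as permanent loss. In study 1302 (Protocol 1.4.2.4), a treated subject was dual/mixed on day 8 and R5-only at all other times, and clonal analysis attributed the result to pre-existing virus. Screening uses the DNA assay, whereas failures above 1000 copies/mL use RNA, so an apparent change can partly reflect the assay.

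**Conclusion.** The gap is real and narrow. As written, loss of future drug options cannot show loss of the CCR5-antagonist class through tropism change, and no other outcome summarises that loss. A near-zero result would be accurate for the resistance it counts and incomplete as a statement about remaining options.

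No size can be given for this trial. The 2 dual/mixed results at failure in CD01 show that the event is worth counting; they do not give its rate. The conclusion rests on the protocol's own use of Trofile as the eligibility test for the class, and on reading the specific listing entries as governing over the general sentence in SAP 8.1. Coverage is by schedule: a subject lost before T10 may have no post-baseline result. The outcome is exploratory, so this should be corrected but does not affect the primary outcomes.

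**What to change.** Keep the resistance count as defined. In SAP 3.2.1 and 8.2.4.2, add a separate line beside it:

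- **Numerator:** subjects R5-only at screening with a dual/mixed or X4 Trofile result at any post-baseline test (T10, T48, virologic failure, 6 and 12 months after failure).
- **Denominator:** subjects R5-only at screening with a reportable post-baseline Trofile result, with the number lacking one shown.
- **Presentation:** number and proportion by assigned dose with an exact 95% CI. The interval is descriptive and needs no test or multiplicity rule.
- **Breakdown:** DNA and RNA results separately, and results that persist at the next available test separated from those that revert or have no later test.

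Replace the listing-only rule in SAP 8.2.4.2 with a listing plus a shift table from screening. Reconcile Protocol 1.4.2.7 with 1.5 on tropism. Also align Protocol 4.3, which names only the RNA assay at the failure visit, with 7.10.10 and 7.10.11, which choose by viral load below or above 1000 copies/mL and leave exactly 1000 uncovered; this affects who has a reportable result.

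The cost is one extra table from samples already scheduled, and possibly a less favourable picture of drug options lost.

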#### 7.10.11 HIV-1 Trofile® RNA Assay

- Frequency of testing: At VF, VF-6mFU and VF12mFU Visits, if last known HIV-1 RNA level is >1000 copies/mL.

#### 7.10.12 HIV-1 Drug Resistance Assay

a. GenoSure Archive Assay

GenoSure Archive assay provides HIV-1 antiretroviral drug resistance data when standard resistance testing cannot be performed due to inadequate plasma viral load.

- Frequency of sample collection: At SV, T1, and T48. Additionally, at VF, VF-6mFU and VF12mFU Visits, if last known HIV-1 RNA level is <1000 copies/mL.

b. PhenoSense® GT

PhenoSense® GT is a combination resistance test for three classes of antiretroviral drugs (i.e., nucleoside/nucleotide, non-nucleoside, and protease inhibitors), that provides both phenotypic and genotypic results from the same blood sample (viral load  $\geq 500$  copies/mL).

- Frequency of sample collection: At VF, VF-6mFU and VF12mFU Visits, if last known HIV-1 RNA level is >1000 copies/mL.

c. PhenoSense Integrase and GeneSeq Integrase testing

PhenoSense Integrase and GeneSeq Integrase testing will be additionally performed in conjunction with PhenoSense® GT, if subject has past exposure to an integrase or in cases where complex drug resistance patterns is known or suspected.

*Samples for PhenoSense® GT (and PhenoSense Integrase and GeneSeq Integrase testing, if collected) will be stored at Lab and will be analyzed only if subject experiences virologic failure.*

### 7.10.13 Blood sample collection for evaluation of potential biomarkers

#### 7.10.13.1 gp120 genotypes

- Frequency of testing: At T1 visit
- To assess the baseline gp120 genotypes from each enrolled subject to identify potential polymorphisms that may decrease PRO 140 susceptibility and may affect response to PRO 140

#### 7.10.13.2 Plasma HIV-1 RNA Single Copy Assay

- Frequency of sample collection: At T1 prior to first treatment administration, T8 and T12 visits
- To assess antiretroviral therapeutic response to PRO 140 regimen

#### 7.10.13.3 Immune Activation Markers

- Frequency of testing: At T1, T48 and VF visit

- Immune activation markers (CRP, IL-6, D-Dimer)

#### 7.10.13.4 PhenoSense® Entry Assay

- Frequency of testing: At T1, T10, T48, VF, VF-6mFU and VF12mFU Visits
  - **Note**: *PhenoSense® Entry will be performed at T1 using the blood sample collected for Tropism at Screening for subjects who are found eligible and enrolled in the study.*
- With AMD3100 (X4 inhibitor drug), Maraviroc and PRO 140 (R5 inhibitor drugs).

#### 7.10.13.5 CCR5 expression levels

- Frequency of testing: At T1 visit
- Flow cytometry and the 2D7 MAb will be used to measure CCR5 expression levels on peripheral blood mononuclear cells (PBMCs)

#### 7.10.13.6 Quest Diagnostics Tropism Assay

- Frequency of testing: At SV or T1 and VF
- Includes:
  - HIV-1 Coreceptor Tropism with Reflex to Ultradeep Sequencing or HIV-1 Proviral Tropism.

*The Quest Diagnostics HIV-1 coreceptor tropism test begins with standard Sanger sequencing of the third variable (V3) loop of the HIV-1 gene, the primary determinant of viral tropism. The next-generation DNA sequencing (ultradeep sequencing [UDS]) is performed if standard sequencing detects only R5 virus. HIV-1 Coreceptor Tropism, Proviral DNA test is used when the plasma viral load is < 1000 copies/mL.*
  - CytoDyn is currently investigating the possibility of developing a more accurate test for detection of poor response to PRO 140 in patients with early breakthrough or virologic failure during the treatment phase of the study.

